4.2. Process of Consent

This study is a retrospective study and therefore it is not feasible to obtain consent. Direct patient involvement is not needed in the study and information will only be gathered from pre-existing data in the patients' medical record. All data will be de-identified to limit the chance of exposure of protected health information (PHI).

5. METHODS AND STUDY PROCEDURES

5.1. Efficacy & Safety Assessments

The electronic medical record system (EPIC) will be used to collect data, including: patient age, gender, weight, height, BMI, race, past medical history (hypertension, diabetes, heart failure, afib/flutter, arrhythmia, history of myocardial infarction, history of CVA, CAD, CKD, dyslipidemia, asthma, COPD, cancer), Charlson Comorbidity Index, hospital length of stay, medical intensive care unit (MICU) length of stay. Prior to admission medications include: beta-blockers, ACE-inhibitors, amlodipine, diltiazem, ARBs, hydralazine, clonidine, hctz, loop diuretics, amiodarone, other antiarrhythmics. Vasopressor types and cumulative doses including: norepinephrine, epinephrine, phenylephrine, dopamine, and vasopressin. Epinephrine, phenylephrine, and dopamine will be converted to norepinephrine equivalents in concordance with other literature: 100 mcg dopamine equivalent to 1 mcg norepinephrine, 1 mcg epinephrine equivalent to 1 mcg norepinephrine, and 2.2 mcg phenylephrine equivalent to 1 mcg norepinephrine.^{5,6} Concomitant medications including: hydrocortisone, inotrope use, crystalloid type and amount, colloid use, albumin use, timing of antibiotics, and sedation choice if given. Clinical information collected include: Peak lactate, MAP, mechanical ventilation, in hospital mortality, 28 and 90 day mortality if available. SOFA score will be calculated as a measure of disease severity.

Study Timeline:

Date	Activity
September 2016	Rush University Medical Center IRB approval
October - November 2016	Data collection
December 2016	Data analysis
January 2017	Study presentation and manuscript preparation

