1. PURPOSE OF THE STUDY AND BACKGROUND

1.1. Hypothesis

- Chronic β -blocker or Angiotensin-Converting Enzyme (ACE)-inhibitor use is associated with decreased cumulative doses of vasopressors administered in the first 48 hours of septic shock

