4. SUBJECT IDENTIFICATION, RECRUITMENT AND CONSENT

4.1. Method Of Subject Identification And Recruitment

The study will be retrospective, and collected data will be a result of routine care. Adult patients 18 years of age or older with septic shock who received treatment with a vasopressor will be assessed for inclusion. Patients will be excluded if they are pregnant, transferred from outside hospital on vasopressor, admitted in cardiopulmonary arrest, prior arrest within 24 hours of admission to RUMC or if they required neuromuscular blockade.

Patients will be reviewed from 01/01/2012 to 08/1/2016. A list of MICU patients will be generated by the corresponding ICD-9 and ICD-10 codes for septic shock. Patients will be stratified into 4 groups: 1) not on either a chronic β -blocker or ACE-Inhibitor, 2) on chronic β -blocker, 3) on chronic ACE-Inhibitor, and 4) on both chronic β -blocker and ACE-inhibitor.

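### Chronic liver disease, chronic hypotension and home oral pressors are not separate fields in 5.1; if they are commoner in the no-drug cohort and raise vasopressor need, the unadjusted ANOVA in 13.2 would credit part of their effect to the drugs

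*Combined protocol and SAP*

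**What the plan says.** Section 5.1 names 13 history conditions: "past medical history (hypertension, diabetes, heart failure, afib/flutter, arrhythmia, history of myocardial infarction, history of CVA, CAD, CKD, dyslipidemia, asthma, COPD, cancer". The home-medication list runs from β-blockers and ACE-inhibitors through to "hydralazine, clonidine, hctz, loop diuretics, amiodarone, other antiarrhythmics". Neither list has an entry for chronic liver disease, chronic hypotension or an oral pressor.

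The same section collects some related information: "Charlson Comorbidity Index, hospital length of stay"; "SOFA score will be calculated as a measure of disease severity"; and "Clinical information collected include: Peak lactate, MAP, mechanical ventilation". It does not say whether Charlson components are kept, when SOFA is scored, or whether MAP includes a pre-admission value. The data list is introduced with open wording: "The electronic medical record system (EPIC) will be used to collect data, including: patient age, gender, weight, height, BMI, race".

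The exclusions in 3.2 and 4.1 do not remove these patients. Section 4.1 begins "Patients will be excluded if they are pregnant, transferred from outside hospital on vasopressor, admitted in cardiopulmonary arrest" and goes on to recent arrest and neuromuscular blockade.

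Section 1.1 predicts that users will have "decreased cumulative doses of vasopressors administered in the first 48 hours of septic shock". Section 13.2 analyses the 48-hour dose with an ANOVA across the four cohorts and post hoc pairwise tests. It names no covariate, matching or weighting.

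**The concern.** The comparison cohort is defined by not taking two classes of drug that lower blood pressure, and the outcome is the amount of drug given to raise it. A patient whose usual pressure is low is a plausible candidate both for being off the home drugs and for needing more vasopressor in shock. That makes low usual pressure a possible common cause of cohort membership and outcome.

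The history list covers several reasons to prescribe these drugs (hypertension, heart failure, atrial fibrillation, coronary disease) and some reasons to withhold one class or the other (asthma, COPD, CKD). It does not separately cover the reason that bears most directly on this outcome.

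An excess of such patients in the no-drug cohort would yield a higher dose there with no drug effect, which is the result the hypothesis predicts. The β-blocker versus ACE-inhibitor contrast could also be distorted if β-blockers are prescribed for liver disease. A field that is never abstracted cannot be adjusted for afterwards without reopening the charts.

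**Working it through.** **The plan's own figure.** Section 13.1 gives N = 180 for a one-way ANOVA with 4 groups, f = 0.25, α = 0.05 and power 0.80. With λ = N × f² = 180 × 0.0625 = 11.25 and df 3 and 176, the critical F is 2.656 and the power 0.804. This reproduces the plan's output. At the planned 4 × 50 = 200, power is 0.848. The point below disputes neither figure.

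**Scale.** If one cohort differs from the other three by d (in SD), then f = d × √(3/16). So f = 0.25 corresponds to d = 0.25 / 0.433 = 0.577 SD, or 5.77 mg on the planning SD of 10 mg in 13.1.

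**Inputs that the documents do not give (assumptions).**
- Prevalence of the unlisted conditions, taken together: 15% in the no-drug cohort against 3% in users (low case), or 25% against 5% (high case).
- Rise in 48-hour dose in patients with such a condition: 0.5 SD (5 mg) or 1 SD (10 mg).
- No drug effect.

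**Bias.** Bias = prevalence gap × dose rise. The bias is carried to the F test by f = bias × √(3/16) and λ = 200 × f², with df 3 and 196 and critical F 2.651.

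| Gap | Dose rise | Bias (SD) | Bias (mg) | Share of 5.77 mg | λ | Rejection |
|---|---|---|---|---|---|---|
| 0.15 − 0.03 = 0.12 | 0.5 SD | 0.06 | 0.6 | 10% | 0.135 | 5.8% |
| 0.25 − 0.05 = 0.20 | 0.5 SD | 0.10 | 1.0 | 17% | 0.375 | 7.3% |
| 0.12 | 1 SD | 0.12 | 1.2 | 21% | 0.54 | 8.3% |
| 0.20 | 1 SD | 0.20 | 2.0 | 35% | 1.50 | 15.1% |

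The noncentral F treats the within-cohort SD as fixed. Simulating 20,000 studies for the two 1 SD rows, with patients carrying or not carrying the condition, gives 8.4% and 14.2%, so the approximation is adequate.

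**If the β-blocker cohort shares the condition.** Let the β-blocker cohort have the same prevalence as the no-drug cohort, with the other two cohorts at the low value. Two cohorts are then raised against two, so f = bias / 2. At a 1 SD rise, f = 0.06 or 0.10, λ = 200 × 0.0036 = 0.72 or 200 × 0.01 = 2.00, and rejection is about 9% or 19%. The bias in the none-versus-β-blocker contrast is then zero, but the overall F test is still inflated and the β-blocker versus ACE-inhibitor contrast takes the bias instead.

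**What the collected data can recover.** On the assumption that a standard Charlson index is used, liver status has to be established to score it. As listed, though, only the index is recorded, so liver disease is pooled with every other component. SOFA is described as a severity measure, so its liver element would mix chronic disease with the acute illness. MAP without a stated time or a pre-admission baseline does not identify habitual hypotension. The gap is therefore partial for liver disease and clearer for chronic hypotension and home midodrine.

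**The case against.** The strongest case against has four parts.

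**The causal chain is not in the documents.** Nothing there says these conditions keep patients off the drugs, gather in the no-drug cohort or raise the dose. This stands, and the point has to be conditional. A reader might infer that the bias favours the hypothesis. The documents do not support that as a fact: liver disease can itself be a reason for a β-blocker, and recorded conditions such as heart failure and CKD may raise the dose among users. The net sign is unknown.

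**The information is partly collected.** A reader might also infer that these conditions cannot be separated from drug exposure at all. That goes too far, because Charlson, SOFA and MAP hold part of the information and the data list is open-ended. But an open list commits no abstractor to a particular field, and pooled scores do not isolate the condition.

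**The larger defect is in 13.2.** With no adjustment for anything, two more fields change nothing by themselves, and adjusting for these two alone could leave the net bias no smaller. This stands and shapes the fix. It does not remove the point, because a later adjusted model could not use fields that were never recorded.

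**The size is modest, and any retrospective list omits something.** At a 0.5 SD rise the rejection rate is only about 6-7%, and nothing in the documents favours 1 SD. That is fair. The reason to single out these conditions is that the cohorts are defined by drugs that lower blood pressure and the outcome is treatment of low pressure.

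**Conclusion.** The point holds in conditional form. Chronic liver disease, chronic hypotension and home oral pressors are not separate fields and neither condition is excluded, while the primary analysis is unadjusted. If these conditions are commoner in the no-drug cohort and raise vasopressor need, part of their effect will be read as a drug effect.

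On the assumed prevalences and dose rises, that part is 0.06-0.20 SD (0.6-2.0 mg), about 10-35% of the difference the study is powered to detect, with rejection of about 6-15% instead of 5%. The prevalences and dose rises are illustrations and estimate nothing about this population. This is a change the sponsor should make because it is cheap and best made before abstraction. It does not show that the study's result would be wrong or which way it would err.

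**What to change.** In 5.1, add two yes/no fields:
- chronic liver disease or cirrhosis, kept separately from the Charlson total;
- documented chronic hypotension or home midodrine.

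In 13.2, pre-specify an adjusted comparison of 48-hour vasopressor dose that includes both fields together with the comorbidities already listed, not these two on their own. Repeat the comparison without these patients as a sensitivity analysis.

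The cost is a little more abstraction time on about 200 charts that are being opened anyway, and a few model terms. The fields should be set before the abstraction period in the study timeline (October-November 2016), since adding them later means returning to every chart. No treatment changes.

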13. DATA ANALYSIS AND MONITORING

13.1. Sample Size Determination

There are limited data for proper evaluation of a sample size. However, there was a smaller presented study that had a dramatic decrease in norepinephrine dose in patients on a β -blockers or ACE-inhibitors prior to admission for patients in circulatory shock of any kind.⁷ Using these data, estimated 48h cumulative mean dose for norepinephrine patients not on anti-hypertensives will be 50 mg (SD = 10) and estimated 48h cumulative mean dose for norepinephrine for beta blocker, ACE-Inhibitor, and beta-blocker + ACE-Inhibitor groups will be 25 mg (SD = 10). Using a 4-way fixed effects ANOVA power calculation with estimated effect size from previous study ($f = 1.08$) the total sample size would be 16

F tests – ANOVA: Fixed effects, omnibus, one-way

Analysis: A priori: Compute required sample size

Input: Effect size f	= 1.0825318
α err prob	= 0.05
Power (1- β err prob)	= 0.95
Number of groups	= 4
Output: Noncentrality parameter λ	= 23.4375020
Critical F	= 3.2388715
Numerator df	= 3
Denominator df	= 16
Total sample size	= 20
Actual power	= 0.9609969

However, the current proposed study is specifically looking at septic shock and the anticipated effect is unknown. Therefore, using a 4-way fixed effects ANOVA power calculation with a medium effect ($f = 0.25$) has a total sample size of 180 patients.

F tests – ANOVA: Fixed effects, omnibus, one-way

Analysis: A priori: Compute required sample size

Input: Effect size f	= 0.25
α err prob	= 0.05
Power (1- β err prob)	= 0.80
Number of groups	= 4
Output: Noncentrality parameter λ	= 11.2500000
Critical F	= 2.6559389
Numerator df	= 3

Denominator df	= 176
Total sample size	= 180
Actual power	= 0.8039869

A list of ICU patients will be generated by the corresponding ICD-9 and ICD-10 codes for septic shock during the inclusion time frame, randomized and screened until reaching the minimum power and equal groups (n = 200, 50 patients in each group)

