13.2. Planned Statistical Analysis

All data will be reported using descriptive statistics with mean (SD) used to describe normally distributed data and median (interquartile range [IQR]) used for non-normal data or data with a significant number of outliers. Distribution of data and assessment of normality will be analyzed. Chi-squared, Fisher's Exact and Student's t-test as appropriate will be used to assess differences among the study cohorts. A 4-way fixed effects ANOVA will be utilized for the primary outcome, cumulative vasopressor dose at 48 hours. *Post hoc* pairwise comparisons will be completed between groups using Bonferroni's, Turkey, or Hochberg's GT2 depending on final group size and variance. Statistical support for data evaluation will be sought out if necessary.

REFERENCES

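### Dose is planned in absolute mg and body weight has no role in the primary analysis, so a weight difference between the cohorts could hide or mimic a dose difference

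*Combined protocol and SAP*

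**What the plan says.** Section 5.1 pools catecholamines and phenylephrine as norepinephrine equivalents, for example "1 mcg epinephrine equivalent to 1 mcg norepinephrine, and 2.2 mcg phenylephrine equivalent to 1 mcg norepinephrine". The sample size section (13.1) is where a unit for the cumulative dose appears: "estimated 48h cumulative mean dose for norepinephrine patients not on anti-hypertensives will be 50 mg (SD = 10"), against "beta blocker, ACE-Inhibitor, and beta-blocker + ACE-Inhibitor groups will be 25 mg (SD = 10"). Sections 1.1, 1.2 and 13.2 speak of cumulative dose or dosing without a unit, and no section gives a per-kg one.

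Weight is among the fields to be extracted (section 5.1: "patient age, gender, weight, height, BMI, race, past medical history"). Section 13.2 then says: "A 4-way fixed effects ANOVA will be utilized for the primary outcome, cumulative vasopressor dose at 48 hours". It adds post hoc pairwise comparisons, but names no covariate, no weight normalisation and no sensitivity analysis. Sections 2.1 and 4.1 form the four cohorts from chronic β-blocker and ACE-inhibitor use.

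**The concern.** The hypothesis is that chronic users receive less vasopressor. Suppose infusions are ordered per kg and the requirement is similar per kg. Two patients with the same requirement then accumulate milligrams in proportion to their weight, and the outcome partly measures body size.

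Nothing in the design balances weight. Section 2.2 says that comorbidities lead to these drugs, so equal weight across cohorts cannot be taken for granted. If users are heavier, a real reduction can be masked, or a difference in mg can appear where there is none per kg. If they are lighter, a reduction can appear that reflects size alone. Either way, the planned ANOVA cannot tell the two apart.

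**Working it through.** **Inputs from section 13.1.** Four groups; α = 0.05; f = 0.25; N = 180 required and 200 planned (50 per cohort); reference mean 50 mg; SD 10 mg.

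**Assumptions not in the documents.** Dose in mg is proportional to weight. The three user cohorts share one mean dose and one mean weight. Users are 10% heavier. The SD is 10, 20 or 30 mg and the same in every cohort.

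**Reproducing the plan.** The test is a one-way fixed-effects F test with λ = N·f² and df 3 and N − 4.
- f = 0.25, N = 180: λ = 180 × 0.0625 = 11.25, critical F 2.6559, power 0.8040. This matches section 13.1.
- f = 0.25, N = 200: λ = 12.5, power 0.848.
- When one mean differs from three equal means by d, f = d·√(3/16)/SD. With d = 25 and SD = 10, f = 25 × 0.4330/10 = 1.0825, which also matches.

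**Effect in mg at f = 0.25.** d = 0.25·SD/0.4330. This is 5.77 mg at SD 10 (11.5% of 50), 11.55 mg at SD 20 and 17.32 mg at SD 30.

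**Hiding a true per-kg reduction, users 10% heavier.** The user mean in mg is (50 − d) × 1.10.

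| SD | User mean | Visible difference | f | Power, N = 200 |
|---|---|---|---|---|
| 10 | 44.23 × 1.10 = 48.65 | 1.35 | 0.058 | 9% |
| 20 | 38.45 × 1.10 = 42.30 | 7.70 | 0.167 | 48% |
| 30 | 32.68 × 1.10 = 35.95 | 14.05 | 0.203 | 66% |

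Without a weight difference, power is 85% in each row. At SD 10, users 5% heavier give 44.23 × 1.05 = 46.44, a difference of 3.56 mg and power of 41%. The weight excess that cancels the effect is 50/44.23 − 1 = 13.1% at SD 10, but 50/38.45 − 1 = 30% at SD 20.

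**Mimicking a difference, same mg/kg in all cohorts, users 10% heavier.** The difference is 50 × 0.10 = 5.0 mg.
- SD 10: f = 5 × 0.4330/10 = 0.217, P(reject) 72%.
- SD 20: f = 0.108, P(reject) 22%.
- SD 30: f = 0.072, P(reject) 12%.

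The nominal rate is 5%. Under strict proportionality the users' SD would also rise by 10%, which would lower these figures somewhat.

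**The opposite case: mg does not scale with weight, but the outcome is divided by weight.** With no true mg difference and users 10% heavier, their mean on the reference scale is 50/1.10 = 45.45, a spurious 4.55 mg reduction.
- SD kept at 10: f = 4.55 × 0.4330/10 = 0.197, P(reject) 63%.
- Users' SD also divided by 1.10: pooled SD √((100 + 3 × 82.6)/4) = 9.33, f = 0.211, P(reject) about 70%.
- Users 5% heavier: 20% and 21% respectively.

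**The case against.** Several stronger readings are tempting, and the documents do not support them.

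- *The outcome is proven to be absolute.* The conversion ratios in section 5.1 would be the same in mcg/kg, and the mg figures in section 13.1 are planning values. Absolute mg is the natural reading, but strictly the unit of the outcome is never defined.
- *The comparison is biased, and against the hypothesis.* That needs dose to scale with weight and the cohorts to differ in weight. The documents give neither the ordering unit nor any weight data. Per-kg ordering is not enough either: if infusions are adjusted to response and the requirement does not rise with weight, a heavier patient ends at a lower mcg/kg rate and similar milligrams. If orders were in mcg/min, the mechanical effect is absent.
- *A modest weight difference wipes out or reverses the effect.* This holds at SD 10 mg. Section 13.1 adopts f = 0.25 as a generic medium effect and ties no SD to it. At SD 20 or 30, users 15% heavier do not reverse the sign, since cancelling the effect takes an excess of 30% or more.
- *The primary outcome should therefore be mcg/kg.* If dose does not scale with weight, that creates a false reduction in heavier users, which favours the hypothesis.

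It can also be said that the planned cohort comparisons in section 13.2 could reveal a weight imbalance. They could, but they would not correct the primary result for it. What stands of the objection limits the size of the problem and the choice of remedy. It does not remove the gap: the unit is not stated and a collected variable that may matter has no planned use.

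**Conclusion.** The point holds as a conditional gap in the analysis plan. Nothing in section 13.2 protects the primary comparison from a weight difference between non-randomised cohorts. If dose is proportional to weight and users are 10% heavier, the loss runs from near-total (SD 10 mg) to moderate (SD 30 mg), and the false-rejection rate from severe to roughly twice nominal. If dose does not scale with weight, the loss and the false rejection both vanish. The documents cannot say which case applies, so the figures are a sensitivity range, not an estimate of bias. The sample size calculation itself is not in question here, and no revised N follows, because the documents give no per-kg SD.

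**What to change.** In sections 5.1 and 13.2:

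1. State that the outcome is cumulative norepinephrine-equivalent dose in mg.
2. Prespecify a weight-adjusted analysis of the 48-hour dose: the ANOVA model with charted weight at vasopressor start as a covariate. This does not assume that dose is proportional to weight.
3. Report the mcg/kg result beside the mg result at 6, 12, 24 and 48 hours.
4. State that a cohort difference will be described as not due to body size only if these analyses agree.
5. Do not make mcg/kg the primary outcome by default.

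Fix this before analysis, so that the scale is not chosen with results in view.

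The cost is a few sentences and a little extra analysis on a field already collected. Charted weight may include resuscitation fluid, and the per-kg result will not be comparable with the 50 mg and 25 mg in section 13.1. Weight adjustment does not deal with other differences between users and non-users.

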5.2. Costs to the Subject

There will be no costs to the subjects as this is an evaluation of pre-existing medical data.

5.3. Payment for Participation

Subjects will not receive compensation for their participation in this study.

6. CONCOMITANT AND DISALLOWED MEDICATIONS

Concomitant and disallowed medications are not applicable to this study design.

7. SUBJECT WITHDRAWALS

Given the design of this study, subject withdrawal will not be an issue encountered.

8. STUDY DRUG/DEVICE/BIOLOGIC ADMINISTRATION/ASSIGNMENT

This study does not involve the implementation of a study drug, device, or biologic.

9. SAFETY AND REPORTABLE EVENTS

Given the design of this study we will not be prospectively collecting adverse events that require reporting.

10. RISK/BENEFIT ASSESSMENT

10.1. Potential Risks

There are minimal risks to the study subjects. The only potential risk is invasion of privacy since medical records will be accessed. All data will be de-identified to limit the chance of exposure of PHI.

10.2. Protection Against Risks

It will be the responsibility of the primary investigator (PI) for data collection and storage in a safe, secure area and password protected computer when identifying eligible patients. Research Electronic Data Capture (REDCap) will be used for data collection and storage. Patient confidentiality will be maintained by recording only de-identified data onto the data collection form. Although the data collected and stored in REDCap will be exported for analysis, the exported data will contain no unique, patient-identifying information.

